Day 0: Subject presents fasting to the CHC. Blood pressure, heart rate, weight, height and waist circumference and body composition on InBody520 BioSpace will be recorded. FitBit® activity monitor placed. Subjects will have a jejunal feeding tube placed by the investigator using a CORPAK EAS™ and will then be randomized to the control or intervention group.

Day 0-Day 14: Subjects will take a mixed meal or electrolyte solution at a prescribed rate and interval and will be requested to eat ad lib only from provided meals of known caloric amount or from a list of low calorie items. Subjects will maintain a log of all food intake, temperature at least daily, tube position and symptoms and blood glucose 4 times a day.

Day 7: The subject will return to the CHC for review for continuation in the study, of their log and caloric intake and for adjustment of medication if necessary and activity monitor download.

Day 14: Day 0 measures will be repeated at the CHC and the tube removed. All uneaten food will be returned for caloric intake determination, activity monitor download.

Day 15-Day 28: The subject will maintain a medication and blood glucose log for 14 days after the removal of the tube.

Day 28: Exit outcome measures similar to those at Day 0.

Safety: The subjects will be monitored for fever, sore throat, displacement of the tube, gastrointestinal upset, vital signs, biochemical measures and weight change, and if pre-specified criteria are met or in the clinical judgment of the PI it is not appropriate to continue, will be withdrawn from the study.

Outcome Measures: weight change, caloric intake, waist and hip measurement, hormones and biochemical measures, physical activity, body composition, select symptoms, medication use, average self-monitored blood glucose level

Reimbursement: Subjects will receive standardized meals of known caloric amount for 2 weeks and up to \$300 cash.

Statistics This is a pilot study and sample size estimates are not appropriate. However based on studies of dietary restriction with a 1250 kcal diet for 1 week we anticipate identifying a significantly greater weight loss in the intervention arm with a sample size of 10 subjects/group. Fifteen subjects/group will be enrolled to allow for drop-outs.

Analysis: Primary analysis will be to compare change from baseline in outcome measures between the 2 groups using paired t-test. SC CTSI Biostatistics Department has aided in the study design.

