Day14: Baseline measures will be repeated. The position of the tube tip will be assessed per FDA approved procedure by reinsertion of the subject’s own transmitting stylet and then removed. All uneaten food will be returned for caloric intake determination, activity monitor download.

Day 15-Day 28: The subject will maintain a symptom and blood glucose log for 14 days after the removal of the tube.

Day 21: Subjects will return to the clinic for review of log and activity monitor. Medications will be titrated at the study clinician’s discretion in an attempt to attain euglycemia.

Day 28: Exit outcome measures similar to those at Baseline and Day 14.

Possible Additional Study Visits: Subjects will be seen at additional visits by the study team if they so request or if deemed appropriate by the study clinicians. Subjects will be encouraged to contact the study team if they do not feel well or if certain criteria are met. These specific criteria are:

- Self monitored blood glucose values over 200mg/dL on 3 scheduled checks
- Failure to ingest prescribed amounts of fluid
- Failure to administer tube feed on 2 successive occasions
- A morning oral temperature reading >37.2°C (98.9°F) or an afternoon temperature of >37.7°C (99.9°F)
- Pain that does not resolve spontaneously over 3 or 4 hours or with use of acetaminophen

Additional visits may be scheduled to determine position of the tube or to reposition the tip if it was not successfully placed in the jejunum at the initial visit or if the tube is blocked in which case attempts will be made to unblock it or it may be replaced.

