5.3 Withdrawal Criteria

- Non-adherence to study instructions by subject for more than 2 days.
- Any request by subject
- Fever over 100.4 F, more than 1 episode of vomiting, gastrointestinal upset not relieved by reduction in tube feed, dislodged anchor or tube, average daily glucose over 200mg/dL on 2 or more days, weight change of >7% in first week of tube use.
- Clinical judgment of the PI (reason to be specified)

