9.0 CLINICAL AND LABORATORY EVALUATIONS AND STUDY CALENDAR

Table 5

	Preparation			With Tube		Follow Up	
	Approximately Day-14	Approximately Day -7	Day 0	Day 7	Day 14	Day 21am	Day 28
Location ALL at EDWARD R. ROYBAL CHC							
Clinical Evaluation	By orthodontist for suitability for molar band	By orthodontist for placement of molar band (may require 2 visits)	By MD Vital Signs Symptoms Physical Exam Weight Waist Hip	By MD Vital Signs Symptoms Physical Exam Weight Waist Hip	By MD Vital Signs Symptoms Physical Exam Weight Waist Hip	By MD Vital Signs Symptoms Physical Exam Weight Waist Hip	By MD Vital Signs Symptoms Physical Exam Weight Waist Hip
Labs (total 20 cc/visit)	none	none	BMP ^a Fasting: Adiponectin ^b Leptin ^b FGF-19 ^b Insulin ^b Glucose ^b C-peptide ^b GLP-1 ^c Ghrelin ^c PYY ^c CCK ^c Bile Acids ^c FT3 ^c		BMP ^a Fasting: Adiponectin ^b Leptin ^b FGF-19 ^b Insulin ^b Glucose ^b C-peptide ^b GLP-1 ^c Ghrelin ^c PYY ^c CCK ^c Bile Acids ^c FT3 ^c		BMP ^a Fasting: Adiponectin ^b Leptin ^b FGF-19 ^b Insulin ^b Glucose ^b C-peptide ^b GLP-1 ^c Ghrelin ^c PYY ^c CCK ^c Bile Acids ^c FT3 ^c
Procedure	Place spacers	Place band	Place tube Place FitBit Body Composition Provide 1 week food	Return all uneaten food Provide 1 week food	Return all uneaten food Remove tube and band Body Composition		Remove FitBit Body Composition
Other Activities	none	Start Daily Flow Sheet	Review daily flowsheet including self-monitored blood glucose	Review daily flow sheet including self-monitored blood glucose Download FitBit/recharge	Review daily flow sheet including self-monitored blood glucose Download FitBit/recharge	Review daily flow sheet including self-monitored blood glucose Download FitBit/recharge	Review daily flow sheet including self-monitored blood glucose Remove and download FitBit
Food Intake	Ad lib		Day 0-Day 14 Tube Bolus and Provided Diet Ad lib free foods Supplements		Day 14-Day 28 Ad lib		

^aat USC DORI ^bat Cedars-Sinai ^cat Cedars Sinai when funds available

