10.0 CRITERIA FOR EVALUATION AND ENDPOINT DEFINITIONS

Primary aim: weight change immediately following the intervention period between the study groups

Secondary aims: to compare the following within and between groups:

- a. From Day 0 to Day 14: caloric intake (as determined by consumption of provided food)
- b. From Day 0 to Day 14: weight change (within group)
- c. From Day 0 to Day 28: weight change
- d. From Day 0 to Day 14 and also from Day 0 to Day 28: waist and hip measurement, hormones and biochemical measures, physical activity, body composition, select symptoms, medication use, average self-monitored blood glucose level

11.0 SPECIAL INSTRUCTIONS:

Samples will be collected by the PI or IRB approved research assistant from peripheral venipuncture.

The investigator will draw 20cc fasting blood at Day 0, 14 and 28 visits into a prepared tube containing aprotinin. This will be kept on ice and centrifuged, separated and aliquoted within 30mins of blood draw. Samples will then be stored at -20 degrees centigrade until transferred on ice to collaborator for assay.

Study Costs: All costs for this study will be paid from study funds. There will be no patient care costs incurred for payment from non-study funds. Costs covered by the study include study visits, supplies, equipment, blood draws, biochemical analysis and subject reimbursement.

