Glucose tablets (generic)	15g	Qty 30

TABLE E: Study Supplies	
Item	Quantity
Blood glucose strips	150
Thermometer	1
Fitbit Activity Monitor	1
Glucose meter	As needed
Glucose meter battery	As needed
Study log	4
Syringe to administer tube feed	15
Tylenol liquid (500mg/15mls)	As needed Maximum 60mls/day
Syringe to administer tube feed	15

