APPENDIX C: FREE TO GO DAILY LOG (TUBE PERIOD)

DATE: STUDY DAY STUDY ID # Page 1/2

GENERAL	SID#:							
	Morning		Midday		Afternoon		Evening	
Time:								
Blood glucose value:								
Throat discomfort or pain 0 (none)-10 (really bad):								
Tylenol taken since last log	Y N	Y N	Y N	Y N	Y N	Y N	Y N	Y N
Temperature (at least once a day):								
Is molar band secure?	Y N	Y N	Y N	Y N	Y N	Y N	Y N	Y N
Is the tube smooth and undamaged?	Y N	Y N	Y N	Y N	Y N	Y N	Y N	Y N
GI upset 0 (none)-10 (really bad):								
Tube feed given	Y N	Y N	Y N	Y N	Y N	Y N	Y N	Y N
Amount tube feed taken by mouth (if any) mls:								
Required oral feed taken	Y N	Y N	Y N	Y N	Y N	Y N	Y N	Y N
Time taken to give tube feed (minutes)								
Tube flushed	Y N	Y N	Y N	Y N	Y N	Y N	Y N	Y N
Multivitamin taken? Y/N	Y N	---	---	---	---	---	---	---
Klor-Con taken Y/N	---	Y N	---	---	---	---	Y N	---
Calcium and Vit D taken? Y/N	Y N	---	---	---	Y N	---	---	---
Additional salt taken? Y/N	---	---	---	---	---	---	Y N	---
Med Taken (name/ dose):								
Med Taken (name/ dose):								
Med Taken (name/ dose):								
Med Taken (name/ dose):								
Med Taken (name/ dose):								
Med Taken (name/ dose):								
Med Taken (name/ dose):								

FOOD AND DRINK*	Morning	Midday	Afternoon	Evening
Item and amount				
Item and amount				
Item and amount				
Item and amount				
Item and amount				

Item and amount				
Item and amount				
Item and amount				
Item and amount				
Item and amount				

*Please use additional sheets if necessary

DATE: _____ STUDY DAY _____ STUDY ID # _____ Page 2/2

COMMENTS

*Please use additional sheets if necessary

FREE TO GO DAILY LOG (BEFORE AND AFTER TUBE PERIOD)

DATE: STUDY DAY STUDY ID # Page 1/1

GENERAL	SID#:			
	Morning	Midday	Afternoon	Evening
Time:				
Blood glucose value:				
Med Taken (name/ dose):				
Med Taken (name/ dose):				
Med Taken (name/ dose):				
Med Taken (name/ dose):				
Med Taken (name/ dose):				
Med Taken (name/ dose):				
Med Taken (name/ dose):				

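### Average self-monitored glucose is taken from the subject's written log; no available staff procedure reads the glucose meter, although the activity monitor is downloaded at the same visits

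*Combined protocol and SAP*

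**What the plan says.** Section 10.0, item d, lists "average self-monitored blood glucose level" among the secondary outcomes, for Day 0 to 14 and Day 0 to 28. Sections 2.0 and 13.0 list it as well.

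The values come from the subject. For the tube period the synopsis states: "Subjects will maintain a log of all food intake, temperature at least daily, tube position and symptoms and blood glucose 4 times a day". For follow-up, Section 3.0 states: "The subject will maintain a symptom and blood glucose log for 14 days after the removal of the tube". The form is the daily log in Appendix C, where the entry is a blank field, "Blood glucose value", with four columns a day.

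Table 5 in Section 9.0 has staff review this sheet at Days 0, 7, 14, 21 and 28. The entry for Days 7, 14 and 21 reads "Review daily flow sheet including self-monitored blood glucose Download FitBit/recharge". At Day 28 the FitBit is removed and downloaded; at Day 0 it is only placed. Section 3.0, for Day 14, again names the activity monitor as the device to download: "All uneaten food will be returned for caloric intake determination, activity monitor download".

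Table E in Appendix A lists "Glucose meter" with the quantity given as needed. Model, memory and return for reading are not stated. Section 12.0 provides histograms or frequency tables, range checks, counts of missing values and cross-tables.

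**The concern.** Two self-worn or self-used devices produce outcome data in this trial. One is read directly. For the other, the available text relies on what the subject copies from the display to paper. Rounding, miscopying and occasional omission are ordinary in a log kept four times a day for weeks.

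Subjects give themselves two different named products, and the route of each defines the arm. No blinding is described, so subjects can be expected to know their allocation. If recording habits differ with that knowledge, the between-arm glucose contrast is shifted. The hypothesis claims improved glycemic control, and Section 13.0 says that effect sizes from this pilot will feed the design of later studies, where a larger sample would not remove such a shift.

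**Working it through.** The plan gives no figure for recording error or for the variability of self-monitored glucose, so there is nothing to reproduce. The check sets the passages side by side and then sizes the effect under stated assumptions.

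**1. Data source**
- Activity: device worn, device downloaded at Days 7, 14, 21 and 28.
- Glucose: meter used, value written by the subject, sheet reviewed at Days 0, 7, 14, 21 and 28. No step in Sections 3.0, 9.0 or 12.0 returns to the meter.

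**2. Volume of entries**
- Tube period: 4 × 14 = 56 readings per subject. To Day 28: 4 × 28 = 112. If four a day begin about Day -7, when Table 5 starts the flow sheet: 4 × 35 = 140. Table E supplies 150 strips, so the schedule is covered.

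**3. What the planned checks would catch**
- Omission. Suppose a subject leaves out every reading above 200 mg/dL. With readings assumed normal, mean 150, 170 or 190 and SD 40, 45 or 50, the mean of what remains is 141.8, 150.8 or 156.2, a fall of about 8, 19 or 34 mg/dL. The share omitted is P(Z > 1.25), P(Z > 0.67) or P(Z > 0.20), that is about 11%, 25% or 42%. Of 56 readings this leaves about 6, 14 or 24 blanks, which log review and the missing-value count should show.
- Miscopying or rounding. A value altered by 10 to 40 mg/dL can stay within any plausible range and leaves no blank. None of the Section 12.0 checks is built to find it.

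**4. Size of the undetected kind**
- Random, undirected errors largely average out. Over 56 readings their contribution to a subject's mean shrinks by √56 ≈ 7.5. Errors of equal average size in both arms cancel in the between-arm difference. Only directional errors that differ by arm bias it.
- Shift = share of one arm's readings lowered × amount lowered. Assumed shares 5%, 10%, 25%; assumed amounts 10, 20, 40 mg/dL. Smallest: 0.05 × 10 = 0.5. Middle: 0.10 × 20 = 2. Largest: 0.25 × 40 = 10 mg/dL.

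**5. Against sampling error**
- SE of the difference = SD × √(2/n), with assumed between-subject SD of the outcome 20, 30 or 40 mg/dL.
- n = 10 per group: 8.9, 13.4, 17.9. n = 15 per group: 7.3, 11.0, 14.6.
- Of the nine share-by-amount combinations, only the largest (10 mg/dL) exceeds one SE, and only at SD 20. The other eight are 5 mg/dL or less and fall below every SE listed.

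**The case against.** The strongest reply is that harm is not shown. This is an exploratory pilot, self-monitored glucose is one of many unranked secondary outcomes, and weight is measured in the clinic. Laboratory fasting glucose at Days 0, 14 and 28 gives a glycemic comparison that owes nothing to subject entries, and Table 5 does not put it among the assays that wait for funds. Both arms have the same log, food and products, so no mechanism for different recording by arm is evident. All of this stands and sets the low priority. It does not remove the point: three fasting values cannot verify an average of four readings a day.

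A reader might also infer more than the documents support:
- *That the meter is never read.* The available text is silent. The Appendix B participant instructions were not available and could ask subjects to bring the meter. What can be said is that the staff procedures seen contain no such step.
- *That subjects are paid to under-record.* The synopsis mentions meals and up to $300 but does not tie payment to glucose values or completion. Motive would be conjecture, and ordinary copying error is enough for the point.
- *That the withdrawal criterion in Section 5.3, "average daily glucose over 200mg/dL on 2 or more days", is defeated.* It names no data source, needs two or more days, and stands beside the investigator's clinical judgment. Sensitivity near a cutoff is true of any cutoff.

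**Conclusion.** The point holds in limited form. In the available text a glycemic secondary outcome rests on subject-written values, while the device that produced them goes unread at visits where another device is downloaded. The planned data checks would show gaps and outliers but not plausible wrong values, so the outcome carries avoidable recording error and possible bias.

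The size is unknown. The illustrative between-arm shift of 0.5 to 10 mg/dL rests entirely on assumed error rates, on errors confined to one arm, and on an assumed SD of 20 to 40 mg/dL. On those assumptions it is probably below one standard error in this pilot. Arm-dependent recording is possible, given that no blinding is described, but nothing in the documents shows it. The primary outcome is not affected. Cheap improvement, low priority.

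**What to change.** - **Table 5, Days 0, 7, 14, 21 and 28:** add to the existing log review a step to download or transcribe the stored glucose meter readings.
- **Appendix A, Table E:** issue one memory-equipped study meter to each subject, from the start of the log to Day 28, so that the pre-tube readings are captured too.
- **Section 10.0:** define average self-monitored glucose from the meter record, with log values as a flagged fallback where no meter reading exists.

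Staff would then also have the meter record when they review glucose for safety at visits. The Section 5.3 withdrawal rule is left as written.

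Cost: a few minutes at each of five visits already scheduled, and at most 30 basic meters (15 per group × 2). The downside is small: readings taken on another meter must be flagged as log-only.

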10.0 CRITERIA FOR EVALUATION AND ENDPOINT DEFINITIONS

Primary aim: weight change immediately following the intervention period between the study groups

Secondary aims: to compare the following within and between groups:

- a. From Day 0 to Day 14: caloric intake (as determined by consumption of provided food)
- b. From Day 0 to Day 14: weight change (within group)
- c. From Day 0 to Day 28: weight change
- d. From Day 0 to Day 14 and also from Day 0 to Day 28: waist and hip measurement, hormones and biochemical measures, physical activity, body composition, select symptoms, medication use, average self-monitored blood glucose level

11.0 SPECIAL INSTRUCTIONS:

Samples will be collected by the PI or IRB approved research assistant from peripheral venipuncture.

The investigator will draw 20cc fasting blood at Day 0, 14 and 28 visits into a prepared tube containing aprotinin. This will be kept on ice and centrifuged, separated and aliquoted within 30mins of blood draw. Samples will then be stored at -20 degrees centigrade until transferred on ice to collaborator for assay.

Study Costs: All costs for this study will be paid from study funds. There will be no patient care costs incurred for payment from non-study funds. Costs covered by the study include study visits, supplies, equipment, blood draws, biochemical analysis and subject reimbursement.

12.0 DATA COLLECTION AND MONITORING

Confidentiality of Discussions: The privacy of the research subject will be protected by having discussions regarding the study and confidential health matters in a private room in the Roybal CHC or by telephone from a private office.

Initial and follow-up Case Report Forms (CRF): All data will be entered on IRB approved clinical medical record forms. All data will be kept in a locked cabinet in [name] office when not in use.

Data Security and Confidentiality Data will only be accessible by the primary investigator and co-investigators and research assistants for the purposes of the study. Data will be transcribed from the CRF to a non-network computer, password protected, accessible only by the investigators for the purposes of the study. Each enrolled patient will be assigned a study number and all data will be stored under this study number with no linkage to patient identifiers. Data will also be stored by [name] in her computer protected computer database using a study specific identifier developed specifically for the study. The computer is password protected and is in a room accessible only to the laboratory personnel. All personnel have been HIPAA trained.

When the study is completed the data or data set will be maintained in a de-identified form on the PI's computer. Identifiers will be destroyed at the earliest opportunity consistent with the conduct of the research and/or clinical needs and will be maintained no longer than 2 years after completion of the study.

Source Documentation and Timeliness of CRF Completion. The CRF will be completed by the research staff daily. Data will be stored on REDCap.

Retention of Study Record: Study data will be retained for 5 years after publication. At this time or in case non-publication, the data will be destroyed.

Data Management: Data will be recorded on clinic record forms and will be entered into a database system for subsequent statistical analysis. Potential data errors will be detected by plotting frequency tables or histograms on outcome and exposure variables and data ranges will be checked to identify potential outliers. The frequency of missing values will be counted for each variable at each of the follow-up time points. Cross-tables will be used to verify the logical validity of related variables.

14.0 REGISTRATION GUIDELINE

14.1 Specify phone number to register the patients: [name].

Subjects will be randomized to caloric or non-caloric jejunal feeding.

Forms and records needed for registration:

- 14.2.1 Informed Consent
- 14.2.2 Daily self-monitoring sheet
- 14.2.3 Visit work sheet

At the time of registration, two copies of a signed and dated patient Informed Consent form with Bill of Rights will be available (an original for patient's medical chart; one copy for the patient; and the other for the PI's file).

15.0 BIOHAZARD COMTAINMENT

Blood sampling and IV line placement will follow standard biohazard safety precautions.

Sharps will be disposed of in clinic sharps containers.

16.0 ETHICAL AND REGULATORY CONSIDERATIONS

All institutional and Federal regulations concerning the Informed Consent form will be fulfilled. The study will be conducted in adherence to ICH Good Clinical Practice.

APPENDIX A: FREE TO GO NUTRITION*Note: If the listed items are not available the PI may authorize similar substitutes*

Item	Amount and Route
Ensure High Protein Shake	800mls/day by tube or mouth as advised
Pedialyte Solution	800mls/day by tube or mouth as advised
Klor-Con10m potassium tablets	2 tablets/day
Table salt	Half a teaspoon/day
Kirkland Signature Daily Multi Vitamins & Minerals:	1 tablet/day
Kirkland Signature Calcium 600 Mg + D3 500 tablets:	2 tablets/day

Item Provided	Brand	#Servings provided	Cals/serving
Oatmeal	Quaker Instant Variety	10	130
Eggs	California Ranch Fresh	10	90
Milk	Real Fresh	12	150
Soft tortilla	Guerrero Flour	48	130
Sliced brown bread	Nature's Own Whole Grain Wheat	22	60
Sliced white bread	Nature's Own Whole Grain White	22	75
Soup	Progresso	10	130
Frozen entrée	Lean Cuisine	10	280
Non-frozen meal	Nissin Bowl	10	280
Canned meal	Campbells Chunky	10	140
Pudding	Snackpack	8	110
Cookies	Quaker Chewy Variety	8	100
Ice cream	Dreyers No Sugar	16	90
Canned fruit	Delmonte Light Variety	8	70
Apples	5 apples (fresh)	5	95
Bananas	5 bananas (fresh)	5	105
Orange juice	Minute Maid	12	140
Frozen Vegetables	Essential	10	40
Water Flavor Enhancer	Dasani Drops (Mixed Berry flavor)	96	0

Vegetables (1 cup raw)	Drinks	Sugar Substitutes	Desserts & Fruits:
Asparagus	Bouillon, clear broth; (no fat)	(ALL sugar free)	Cranberries
Bean sprouts	Diet or Sugar free soda	Hard candy and gum	Lemons
Beet greens	Diet or Club soda	Gelatin	Condiments
Broccoli	Coffee/tea	Jam/Jelly	1 tablespoon ketchup or mustard
Brussels sprouts	Sugar free drink mixes	1-2 tablespoon pancake syrup	Unsweetened pickles
Cabbage, (all kinds)			
Chard			
Cauliflower			
Celery			
Chicory			
Collard greens			
Cucumbers			
Egg plant			
Endive			
Escarole			
Green beans			
Green onion			
Kale			
Lettuce (all kinds)			
Mushrooms			
Mustard greens			
Okra			
Peppers (green or red)			
Radishes			
Spinach			
Squash, summer			
Tomatoes			
Turnip greens			
Watercress			
Wax beans			
Zucchini			

Lemon juice Tomato juice Vegetable juice	Sweet 'n Low or Equal 2 tablespoon whipped topping	2 tablespoon low calorie salad dressing 3 tablespoon taco sauce
--	---	--

TABLE D: Provided. To be taken for hypoglycemia (Low blood glucose) or if concerned that sugar is low.		
Glucose tablets (generic)	15g	Qty 30

TABLE E: Study Supplies	
Item	Quantity
Blood glucose strips	150
Thermometer	1
Fitbit Activity Monitor	1
Glucose meter	As needed
Glucose meter battery	As needed
Study log	4
Syringe to administer tube feed	15
Tylenol liquid (500mg/15mls)	As needed Maximum 60mls/day
Syringe to administer tube feed	15

